### **Description of Study Intervention and Outcome**

The intervention is dexamethasone at 0.15mg/kg while the active control is dexamethasone at 0.6mg/kg. The primary outcome is return visits or readmissions to the hospital within 7 days following initial presentation to the ED with croup. The secondary outcome is AEs following treatment with either of the 2 doses of dexamethasone within 7 and 30 days of treatment (Appendix A).

### **Risks**

The risks participants of this study may be exposed to are risks related to the use of dexamethasone for clinical care of children with croup. Participant's assigned group may end up being less effective or have more side-effects than the other group. Participants assigned to receive 0.15mg/kg may be at risk for incomplete response compared to those in the active control group. The study will not involve any change from the way the child would have been treated and/or managed if not participating in the study. AEs such as GI bleeding, pneumonia, sepsis including bacteria tracheitis have been associated with glucocorticoid bursts. Additional risk may arise relating to the collection of personal health information. However, there are measures in place to keep these risks as minimal as possible.

Lifestyle modification: This is not applicable.

### **Screen failure:**

Eligible participants will be screened at triage as part of standard care for any clinically significant known hypersensitivity to dexamethasone and/or excipients, OraBlend citrus or OraBlend citrus sugar free. As a form of quality check, we will screen all enrolled participants to confirm they were appropriately screened for eligibility at time of enrollment. We will re-assess the patients' sex, age (months), eligibility criteria, and consent status. This second level of screening is to allow reporting according to the non-inferiority CONSORT guidelines (33). Patients will not be rescreened within the same ED visit but will be rescreened on subsequent ED visits for the same croup episode.

### Vanguard RCT recruitment process and sample size estimation:

Based on the budget allocated for patient recruitment (**see attached budget**), sampling of children with clinical diagnosis of croup who presented to the WCH ED between January 2021 and January 2022 (**n=710**), and our experience from a similar trial that used 720 children (34), we plan to recruit 50 children within a year for this vanguard trial (Figure 1). **We will enrol 50% (25 children, in ratio 60:40% male to female) per treatment arm and assess for missing data and protocol adherence.** We will leverage a Bayesian elicitation process used by our team for an ongoing trial on bronchiolitis (35). We will elicit the probability of return visits or readmissions to ED within 7 days for each dose of dexamethasone at 0.15mg/kg versus 0.6mg/kg. The probabilities of revisits or readmissions to the ED closely reflect clinical decision making. We will then use bivariate elicitation to understand the relationship between the two probabilities (36, 37).

### Dexamethasone oral preparation:

The dexamethasone suspension base consists of 1mg/mL oral suspension of dexamethasone with citrus flavored syrup. Dexamethasone 0.25mg/ml oral suspension will be compounded for intervention group. Dexamethasone 1mg/ml oral suspension will be compounded for the control group. To aid blinding, the preparations will be compounded and pre-packaged in identical bottles by the Pharmacy. The preparations will not be distinguishable by appearance, volume, weight, taste, or smell and will be packaged in identical bottles sequentially numbered, sealed, and delivered in opaque bags. **The intervention group will receive oral dexamethasone at 0.15mg/kg (maximum dose 3mg). The active control group will receive oral dexamethasone at 0.6mg/kg (maximum dose 12 mg).** Patients will be observed for 30 minutes, if diagnosed with mild croup, and 4 hours if diagnosed with moderate or severe croup, and if vomiting occurs, one additional dose will be administered.

### Recruitment, blinding, and withdrawal:

Potential participants will be screened and enrolled consecutively after obtaining consent (**Appendix C, Appendix D and Appendix E**). Blinded parties will include the participant, caregiver, research nurse, research assistant, study coordinator, outcome assessors and principal investigators. The research nurse/research assistant will perform recruitment, consent and maintain the master list. Participants will be able to withdraw from the study at any time upon request. However, data accrued from the participant to the time of withdrawal will be retained for analysis. We have designed the baseline and follow-up case report forms (CRFs) (**Appendix F and Appendix G**) to capture the data to be developed in REDCap. We will follow the standard accepted method of reporting noninferiority RCT (42). We have developed a pharmacy manual (Appendix H) with monographs (Appendix I) and manual of operation (MOP – Appendix J) to help guide this study.

## MEASURES TO MINIMIZE BIAS: RANDOMIZATION AND BLINDING

### Randomization

Computerized randomization will be performed by a statistician at the George and Fay Yee Centre for HealthCare Innovation to generate the randomization list. We will perform a computerized randomization in REDCap stratified by age (Figure 1). We will do a block randomization with random

blocks of undisclosed block sizes over the seasons to ensure that we get temporal distribution of croup cases. We will randomly assign patients into either the intervention or control in ratio 1:1. This process will help to reduce bias due to selection and residual confounding that may bias our results. Because croup season peaks over the fall and winter months in Canada, our randomization will consider this factor such that each arm will have an almost similar number per the peak season. While croup is common between 6 months and 5 years, a typical croup affects children between 6 months and 3 years. Based on this, we will randomize such that this age category (6 months-3years and >3 years – 5 years) has almost similar distribution in each arm.

### Sequence Generation

A statistician (not otherwise involved in the study) at the George and Fay-Yee Centre for HealthCare Innovation will develop and maintain a computer-generated permuted-block randomization list, stratified by age. The randomization list will be sent to Pharmacy, where the list will be used to compound and label pre-packaged bottles numbered sequentially.

### Allocation concealment

To ensure concealment, dexamethasone for the two groups will be packaged in an identical manner. The dexamethasone suspension base consists of either 1mg/mL oral suspension or 0.25mg/ml of dexamethasone with citrus flavored syrup. The preparations will not be distinguishable by appearance, volume, weight, taste, or smell and will be packaged in identical bottles sequentially numbered, sealed, and delivered in opaque bags. In the case of an emergency, participant's allocation will be unblinded.

### Masking Procedures

All study personnel (including study coordinators, research nurse, research assistant, investigators) and patients/families will be blinded to the study group assignment. The pharmacists and statistician will be aware of participant assignment but will not be involved with research activities (participant enrolment, data collection, data entry or follow-up).

Details of allocation concealment are outlined above.

### Unblinding Procedures

Data Safety Monitoring Board (DSMB): The DSMB may request unblinding if they deem it necessary to consider the results of the interim safety analysis or to review possible AEs. The DSMB may also request the pharmacist to reveal the patient's group allocation to examine possible adverse events.

Urgent unblinding: In the event of an emergency, unblinding will be performed upon request. The pharmacist, who will maintain the randomization list, will be sent the kit number dispensed to help determine the dose of dexamethasone received by the patient. As the Investigational Drug Service (IDS) Pharmacy hours are Monday to Friday 0800 – 1600H, code break outside of regular working hours will be performed by Pediatric Intensive Care Unit (PICU) Pharmacy. IDS Pharmacy to send the final randomization list to PICU Pharmacy to assist with unblinding requested outside IDS Pharmacy hours. All instances of unblinding will be documented (including reason for unblinding; SAEs,

protocol deviation, etc.) and reported to the University of Manitoba Biomedical Research Ethics Board, the Research Service of Shared Health and Health Canada. Circumstances that may require urgent blind breaking would include clinical symptoms that could be related to the study medications (such as evidence of gastrointestinal bleeding and febrile convulsion). Any unblinding decision will be considered an unanticipated problem and as such will be documented and reported to the DSMB. The plan for treating clinicians to change or stop treatment with either of the two doses will not warrant breaking of the study blind but will result in stoppage or changing of the patient's medication. Following locking of the database and completion of the primary analysis the statistical team will be unblinded.

## STUDY ASSESSMENTS AND PROCEDURES

### Efficacy Assessments

Baseline Measurements: Data regarding age, sex, weight, date of presentation, croup severity, symptoms at ED presentation, onset of symptoms, length of ED stay, discharge date, hospitalization due to croup, length of hospitalization, dose of dexamethasone, other medications (such as epinephrine, antibiotics) and the doses administered, will be collected at baseline and recorded in the Baseline CRF. We also estimate eligibility criteria and recruitment rate.

### Measurements in the ED:

Patients will have vital signs such as temperature, respiratory rate, heart rate, and oxygen saturation measured prior to receiving their oral study medication (time 0). Blood pressure will be measured at enrolment when possible (blood pressure measurements can be difficult to obtain in crying infants). Triage ED temperature measurement (rectal, otic, temporal or axillary) will be used as the baseline temperature. The research nurse will record measurements on in the baseline CRF. Information regarding side effects, co-interventions, length of stay and disposition will be recorded throughout the intervention period in the ED. Patients will be monitored for 30 minutes if mild croup or 4 hours if moderate or severe croup following administration of the oral medication or until discharge (whichever is first) after the first study medication.

### Follow-up measurement in the ED:

The participants' parents/caregivers will not be followed up by either email or telephone following enrolment. However, the outcome assessors will collect data from patient's electronic medical records (EMR) per the follow-up CRF. The follow-up data will include date of initial presentation to ED, date of discharge at initial presentation to ED, number of return visits to the ED with 7 and 30 days, croup severity, symptoms at ED presentation, onset of symptoms, length of ED stay, discharge date, hospitalization due to croup, length of hospitalization, dose of dexamethasone, other medications (such as epinephrine, antibiotics) and the doses administered, AEs associated with the medications, will be collected at follow visits and recorded in the Follow-up CRF. We will also estimate the retention rate.

**Chart Review:** A research team member will review each participant's hospital chart once the 30-day follow-up period has elapsed to examine return ED visits, admission to hospital, diagnosis for any hospital visit, any corticosteroid treatment in hospital. All children with an admission diagnosis of croup will be considered to have been admitted for croup. All charts where an admission diagnosis is other than croup will be reviewed by the site coordinator in conjunction with qualified site investigator to determine reason for admission. We will define admission to hospital as per ICD-10 (Appendix A).

### **Phase 3: Patients' engagement in designing and implementing the vanguard RCT.**

We will **engage 6 patient partners (in this case parents) from our existing patient partner network at CHRIM with lived experience of bringing a child with croup to the WCH ED and other centers (Innovation 2).** One of the patient partners will be embedded in the research team, joining monthly meetings to ensure the patient voice is considered throughout the process. There are no anticipated physical risks for parents/care providers of croup patients. However, asking questions about their experience with children who had croup may be traumatic and emotionally challenging. As such, we will monitor symptoms of emotional trauma such as agitations, nervousness, anxiety, headache and crying spells. We will provide support numbers and organizations should any of the patients need any form of help while participating in this study.

**Year 1:** To plan for this study, we collected [name]'s experience with her two children who had croup. We know from these conversations with [name] that specific symptoms are more bothersome and worrisome for families than others, so we want to ensure that we are tracking these particularly. The ideas that come up will be incorporated into data analysis and interpretation plan of chart review, including giving input on how to use and share this data and what results to prioritize for the vanguard RTC.

**YEAR 2:** Patient partners review and provide comments on the consent forms, scripts, and other documents that will be used to approach patients for recruitment into the definitive RCT. The researchers will continually consult with patients through [name], attending monthly and three dedicated family partner meetings. We want to ensure research questions reflect patient priorities, the methods work for the patient population, and that patient facing documents are appropriate. The family partners will also support grant writing for the definitive RCT.

**YEAR 3:** The family partners will support the vanguard RCT as needed, interpret the data as it becomes available and support grant writing for definitive RCT to ensure family priorities are considered.

### **Definitive RCT:**

Our PICO criteria for the definitive trial as well as the design including the sample size and the proportion of patients to be enrolled in the intervention and control will be based on the findings from the Bayesian elicitation exercise and recommendation from patients with lived

experience. However, we know that our **PICO** would be the same as the vanguard RCT.

### Adverse Events and Serious Adverse Events

Definition of Adverse Events: As per GCP, the definition of an **AE** is as follows: “Any **untoward** medical occurrence in a patient or clinical investigation subject administered a pharmaceutical product and which does not necessarily have a causal relationship with this treatment.” GCP defines an **Adverse Drug Reaction (ADR)** as: “all noxious and unintended responses to a medicinal product related to any dose should be considered adverse drug reactions. “

Definition of Serious Adverse Events: A **Serious Adverse Event (SAE)** and a **Serious Adverse Drug Reaction (SADR)** will be defined as any **untoward** medical occurrence that:

- results in death.
- is considered a life-threatening event (patient at imminent risk of death);
- results in a persistent or significant incapacity or substantial disruption of the ability to conduct normal life functions.
- prolongs an existing hospitalization; and
- is an Important medical event that may not result in death, be life-threatening, or require hospitalization, but may be considered serious when, based upon appropriate medical judgment of the qualified site investigator, they may jeopardize the participant and may require medical or surgical intervention to prevent one of the outcomes listed in this definition.

Classification of an Adverse Event: All AEs will be classified according to **MedDRA (Medical Dictionary for Regulatory Activities)** – a multilingual standardized international medical terminology dictionary used for “regulatory communication and evaluation of data pertaining to medicinal products for human use.”

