## **RATIONALE**

**Adverse events:** A recent self-controlled case series study with over **4 million children** examined the potential harms of corticosteroid bursts (defined as courses of oral corticosteroids for 14 or fewer days) (9) and found that the most common indications for prescription of corticosteroid bursts were acute respiratory tract infections (including croup syndrome) and allergies (9). Of the AEs investigated, **GI bleeding, pneumonia, and sepsis (including bacteria tracheitis)** were directly associated with glucocorticoid bursts. The incidence rate differences per 1000 person-years between children administered a single corticosteroid burst and those not prescribed corticosteroids were 0.60 (95%CI, 0.55-0.64) for **GI bleeding**, 9.35 (95%CI, 9.19-9.51) for **pneumonia**, and 0.03 (95%CI, 0.02-0.05) for **sepsis**. Likewise, another case-control study (10) that was not statistically significant but clinically relevant sounded a note of caution on a possible increase in cases of **disseminated/complicated varicella zoster infection** with recent corticosteroid use.

**Bronchopneumonia and bacteria tracheitis** have been reported in patients treated with dexamethasone at 0.6mg/kg versus 0.15mg/kg in a randomized controlled trial (RCT) (11). Parker et al. (12) reported increased vomiting and febrile convulsion with dexamethasone at 0.6mg/kg. To date, the trials that reported on the AEs associated with using dexamethasone at 0.6mg/kg are limited, inconclusive, **but suggest that a low dose may be associated with fewer AEs (11-15).** All the RCTs were based on the frequentist approach (11-15), **which is prone to error of misinterpretation.** Bayesian methods are an alternative to the frequentist, i.e., the standard null hypothesis significance testing (NHST) framework, and they have advantages.

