#### Time Period and Frequency for Event Assessment and Follow-Up

AEs will be collected from the time the participant is consented until the participant has completed the study. The occurrence of an AE or SAE may come to the attention of study personnel during the ED enrolment visit, during the ED chart review, by a participant's caregiver contacting the study team, or finally by review by a study monitor. SAEs that could be related to dexamethasone (Appendix A) will be specifically solicited from participants' parents/caregivers on revisits. Participants will be followed for 30 days from the date of enrolment for adverse events.

All AEs will be captured on the follow-up CRF in REDCap. Information to be collected includes

an event description, date of onset, clinician's assessment of severity, relationship to study product (assessed by the qualified site investigator), and date of resolution/stabilization of the event and event outcome (resolved/recovered, recovered with sequelae, not recovered/not resolved, death and unknown). All AEs will be followed to adequate resolution or until the Qualified Site Investigator deems the event to be chronic or the participant has been deemed clinically stable.

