#### Croup disease-related events:

Disease related events that are not concluded to be related to the study drug by the Site Qualified Investigator and are part of the natural history of croup will not be reported as AEs (although they will be captured as part of study data collection):

- Hospitalization related to croup.
- The use of IV or NG rehydration for maintaining fluid balance related to croup.
- Cough, difficult breathing.
- Apnea.
- Intensive care admission related to croup; and
- Use of respiratory supports (such as supplemental oxygen, high flow nasal cannula, CPAP, and intubation/mechanical ventilation) in the treatment of croup.

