### Serious Adverse Event Reporting

The Qualified Site Investigator will report any SAE, whether or not considered study intervention related, and any SADR to the Sponsor-Investigator within 72 hours of becoming

aware of the event. The Qualified Site Investigator will complete a “Serious Adverse Event/Drug Reaction Report Form”. The Qualified Site Investigator will include an assessment of whether there is a reasonable possibility that the study intervention caused the event and whether the treatment was given, withheld, discontinued. Any additional requested information from the DSMB or Sponsor-Investigator should be completed as soon as possible. The site will report SAE/SADRs to UoM REB in accordance with the SAE/SADR reporting requirements. The Sponsor-Investigator will also inform the DSMB of the information provided from the site as soon as possible but no later than 7 days after the initial reporting.

If the SAE or SADR are also **unexpected**, the Sponsor- investigator will also file a Serious Unexpected ADR report with Health Canada:

- where the AE/ADR is neither fatal nor life-threatening, within 15 days after becoming aware of the information.
- where the AE/ADR is fatal or life-threatening, immediately where possible and, in any event, within 7 days after becoming aware of the information; and
- within 8 days after having informed Health Canada of the SAE/SADR, submit as complete as possible, a report which includes an assessment of the importance and implication of any findings.

In addition, the Sponsor-Investigator will notify the Site Investigator of SAE and SADR that are also **unexpected**:

- where the AE/ADR is neither fatal nor life-threatening, within 15 days after becoming aware of the information; and
- where the AE/ADR is fatal or life-threatening, immediately where possible and, in any event, within 7 days after becoming aware of the information.

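### The serious adverse event definition omits an event that requires a new hospital admission, and adding it means settling how the croup-event exemption fits with SAE reporting

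*Combined protocol and SAP*

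**What the plan says.** Under Adverse Events and Serious Adverse Events, an SAE is an untoward medical occurrence that meets one of five criteria: death; a life-threatening event; lasting or significant incapacity, or major disruption of normal functioning; an event that "prolongs an existing hospitalization; and"; or an important medical event. The last is left to the investigator's judgment and is described as one that "is an Important medical event that may not result in death, be life-threatening, or require hospitalization", but that may need intervention to prevent one of the listed outcomes.

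Under Time Period and Frequency for Event Assessment and Follow-Up, "Participants will be followed for 30 days from the date of enrolment for adverse events". The same section says that "SAEs that could be related to dexamethasone (Appendix A) will be specifically solicited from" parents or caregivers at revisits.

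Under Serious Adverse Event Reporting, the site investigator "will report any SAE, whether or not considered study intervention related, and any SADR to the Sponsor-Investigator within 72 hours" of becoming aware. Notice to the DSMB, ethics board reporting and, for unexpected events, regulatory reporting follow from that.

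Under Croup disease-related events, events not judged drug-related and "part of the natural history of croup will not be reported as AEs", though they are still captured as study data. Six event types are listed. They include hospitalization for croup, apnea, respiratory support up to intubation, and "Intensive care admission related to croup; and".

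**The concern.** The list contradicts its own last item. The important-medical-event criterion is meant to catch events that fall short of the other outcomes, and it names needing hospitalization as one of those outcomes. That outcome is not in the list.

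The gap falls where this trial is exposed to it. Measurements in the ED sets monitoring at 30 minutes for mild croup and 4 hours for moderate or severe croup, or until discharge if sooner. An event that begins after discharge has no existing stay to prolong. The Risks section names gastrointestinal bleeding, pneumonia and sepsis as associated with glucocorticoid bursts. A later admission for one of these may not be life-threatening, and its status would then rest mainly on one person's judgment.

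At stake is the speed and consistency of safety reporting, not the efficacy analysis. Two investigators could classify the same admission differently, and only one of them would start the SAE reporting clocks.

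**Working it through.** No statistical calculation applies. The check is a reading of the criteria and of what depends on them.

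**Step 1: does any criterion cover a new admission?**

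| Criterion | Covers a discharged child later admitted with an AE? |
|---|---|
| Death | Only if fatal |
| Life-threatening | Only if there is imminent risk of death |
| Incapacity or major disruption of normal functioning | Only if the investigator applies this wording |
| Prolongs an existing stay | No; there is no stay to prolong |
| Important medical event | Only by investigator judgment |

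Criteria that cover a new admission as such: 0 of 5.

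**Step 2: what depends on SAE status?** All of the following come from Serious Adverse Event Reporting.

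- Site to Sponsor-Investigator: 72 hours, that is 3 days, from awareness.
- Sponsor-Investigator to DSMB: at most 7 days after the initial reporting. If that means the site's report, the longest delay is 3 + 7 = 10 days from awareness.
- Site to ethics board: under the board's SAE rules, with no time given.
- If unexpected: Health Canada and the Site Investigator. An event that misses the death and life-threatening criteria falls under the 15-day limit for both.
- A fuller report within 8 days of having informed Health Canada.

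**Step 3: what still applies if the event is not an SAE?**

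- Adverse Event Reporting: AEs are tabulated and reported to the DSMB and the ethics board. The timing is left to the Manual of Operations, which is not among the documents supplied.
- The DSMB section: a meeting at 50% enrolment (25 of 50 children), with a blinded interim safety report.
- Unanticipated Problems: 15 days to the Sponsor-Investigator for a problem that is not an SAE. The event must be unexpected, at least possibly related, and suggest more risk than was known. All three are required, and a risk already named in the protocol may fail the first or the third.
- Unblinding Procedures: gastrointestinal bleeding and febrile convulsion may lead to urgent unblinding, and any unblinding is reported to the DSMB.

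**Step 4: what would an admission criterion do to the croup exemption?** The exemption for croup events turns on the event being judged unrelated. The SAE rule applies whether or not it is related. Neither section refers to the other, and neither Adverse Event Reporting nor the DSMB section makes an exception for croup. The overlap already exists: an intensive care admission or an intubation for croup can meet the life-threatening criterion in some children. An admission criterion would widen it to hospitalization for croup. Three periods need an answer:

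- the index visit;
- days 1 to 7, when a readmission also counts toward the primary outcome;
- days 8 to 30, that is 30 − 7 = 23 days of AE follow-up outside the primary-outcome window.

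**The case against.** The strongest reply is that the gap is narrower than a bare count suggests. The important-medical-event criterion and the wording on disruption of normal functioning let an investigator class many admissions as serious, and the AE and unanticipated-problem routes remain. This stands, and it limits the consequence. It does not repair the definition, because it replaces a fixed criterion with judgment. Soliciting dexamethasone-related SAEs at revisits does not repair it either: that says which SAEs to ask about, not what makes an event serious.

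A reader might infer that such admissions would escape safety oversight. The documents do not support that, for the reasons in step 3 of the working.

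A reader might also infer that the croup exemption suppresses reports of life-threatening croup. That too goes beyond the text. The exemption sits among the AE reporting rules, an SAE is a kind of AE, and its list already contains grave events, so it can fairly be read as a specific exception to the general SAE rule. Read literally, the SAE rule still captures such events. Either way the data are collected. What is missing is a statement of which rule governs.

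A third inference concerns vomiting. The Rationale says a trial "reported increased vomiting and febrile convulsion with dexamethasone at 0.6mg/kg", and vomiting is not among the nine AEs in the Protocol Summary. That list names secondary endpoints. All AEs go on the follow-up form, and absence from the list has no bearing on whether an event is serious.

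The Manual of Operations, the SAE report form and the DSMB charter were not supplied and may add detail. A bullet lost when the PDF was read cannot be wholly excluded, though the list reads as complete.

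**Conclusion.** The omission is real and should be fixed. No SAE criterion covers a new inpatient admission, and the definition's last item presupposes one. As written, an admission after discharge enters SAE reporting only through another criterion or through judgment; if it does not, the limits in step 2 do not apply.

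The unclear relation between the croup exemption and the SAE rule is a smaller point. It is mainly a reconciliation that must accompany the new criterion.

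The size can be stated only in terms of rules. The documents give no rate of admission with an AE, so the number of children affected cannot be estimated. The 23 days are calendar days, not a share of risk. The trial enrols 50 children at one site with a single planned dose, so few events are likely to turn on this, but each would be a safety report. The conclusion assumes that the list as supplied is complete. A manual might guide staff, but the protocol's own definition should be complete without it.

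**What to change.** Add to the SAE list a criterion for an event that requires inpatient hospitalization.

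In the same change, reconcile Croup disease-related events with the SAE definition, Adverse Event Reporting, Serious Adverse Event Reporting and the DSMB section. State whether a croup event judged unrelated to the drug that meets an SAE criterion is reported as an SAE or is exempt. Say so separately for croup admissions at the index visit, within the 7-day primary outcome, and on days 8 to 30. Which way to decide is for the sponsor. Check that the Manual of Operations and the SAE form match.

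The cost is one bullet and one or two sentences, plus a few more SAE forms. The forms stay few if croup admissions already captured as outcomes are exempted. The two changes belong together: the bullet alone would make every croup readmission counted in the primary outcome a candidate SAE.

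The change will not make the site aware of events sooner. Follow-up is through the medical record, without email or telephone contact, and the 72 hours run from awareness.
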